Both the developed model and the comprehensive DHA will be validated in order to test their robustness, transferability and generalizability. Two consecutive validation strategies will be employed respectively: the internal and external validation techniques. We estimate a total number of \approx 420 NSCLC cases to start the validation process. This process will include both internal and external validation. The internal validation step will be focused mainly on techniques such as K-fold cross validation. This will allow to achieve a Transparent Reporting of a multivariable prediction model for Individual Prognosis Or Diagnosis (TRIPOD) level 2b. At this TRIPOD level, data are non-randomly split (e.g., by location or time) into 2 groups: one to develop the prediction model and the remaining dataset to evaluate its predictive performance. In the case of suboptimal performances, all the failing models will be reverted back to the previous stage and the models will be retrained with new specifications in order to increase their robustness. At this point, the models can be validated using external datasets, reaching TRIPOD 3 and 4 levels (External validation). Finally, when the models reach a TRIPOD 4 level, data transferability and full actionability will be granted, allowing the successful and safe application of the model in the clinical Routine (T3.3).

ETHICAL CONSIDERATIONS

Considering the technicality and complexity of the LATERN Project, consortium partners are well aware of the various ethical and legal questions relating to the project. The main ethical issues related to this project include:

the respect for persons and for human dignity; fair distribution of benefits and burden; the rights and interests of the participants; the need to ensure participants' informed consent; processing of personal data; concerns involving the development, deployment and/or use of artificial intelligence (AI)-based systems or techniques.

Protocol LANTERN_v1.0 del 16.12.2022

Therefore, LATERN partners will identify and implement a comprehensive set of ethical and legal requirements in accordance with Declaration of Helsinki principles to ensure compliance for all activities of the project. Appropriate ethical monitoring systems will also be set up.

To this effect, LATERN will implement the following activities:

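### The internal validation step is credited with TRIPOD level 2b, but K-fold cross-validation alone does not give the non-random split by which the plan defines 2b, and no such split is specified

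*Combined protocol and SAP*

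**What the plan says.** The point lies in three consecutive sentences of the combined protocol and SAP, section Predictive model validation. The method: "The internal validation step will be focused mainly on techniques such as K-fold cross validation". The level credited to it: "This will allow to achieve a Transparent Reporting of a multivariable prediction model for Individual Prognosis Or Diagnosis (TRIPOD) level 2b". The meaning of that level: "At this TRIPOD level, data are non-randomly split (e.g., by location or time) into 2 groups", namely "one to develop the prediction model and the remaining dataset to evaluate its predictive performance".

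The section then makes this step a gate. If performance is suboptimal, "all the failing models will be reverted back to the previous stage and the models will be retrained with new specifications". After that, "At this point, the models can be validated using external datasets, reaching TRIPOD 3 and 4 levels". The strongest claim comes last: "when the models reach a TRIPOD 4 level, data transferability and full actionability will be granted". The section expects about "420 NSCLC cases to start the validation process", a count that covers internal and external validation together.

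Two other places bear on the point. Statistical analysis methodology names a training set, a validation set for tuning and a test set. The test set is described as independent of the training set but drawn from the same distribution. Predictive model development names K-fold cross-validation as the means of tuning hyperparameters.

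**The concern.** The plan attaches a named level of evidence to a method and then describes that level in terms the method does not meet. Under the plan's own description, 2b means that performance was checked in a group set apart from development on a non-random basis such as site or calendar time. K-fold is a legitimate internal method, but it answers a different question: how well the modelling procedure predicts cases drawn from the same pool.

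At stake is the meaning of the gate between development and external validation. A model could pass on K-fold results and be reported as 2b, and a reader would take this to mean that it had held up in a different centre or period when no such comparison had been made. Because failing models go back for re-specification, it also matters which cases are protected from that loop, and the plan does not say.

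**Working it through.** The plan states no figure to reproduce here. The check sets its definition of 2b beside the methods it names.

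**Inputs**
- Internal method: mainly K-fold, K not given (Predictive model validation).
- Definition of 2b: two groups, split non-randomly, one to develop and the other to evaluate (same section).
- Test set: independent of training, same distribution; no size, allocation rule or boundary (Statistical analysis methodology).
- Counts: 600 enrolled (Statistical analysis methodology); about 300 with complete data to start modelling (Predictive model development); about 420 to start validation (Predictive model validation).

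**Step 1. What ordinary K-fold supplies.** Each case lies in one fold. It is tested once, when that fold is left out, and is used for fitting in the other K − 1 rounds. Taking K = 5 and K = 10 as illustrations:
- K = 5: tested once, used in 5 − 1 = 4 fits.
- K = 10: tested once, used in 10 − 1 = 9 fits.

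The number of cases inside the K-fold step that are used in no fit is 0 in both, whether 300, 420 or 600 cases enter. This count describes the K-fold step, not the whole plan.

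**Step 2. Side by side with the definition.**

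| Element of 2b as the plan defines it | Ordinary K-fold | Named test set |
|---|---|---|
| Two groups, one developing and one evaluating | No: cases take both roles in turn | Possibly: independent of training |
| Split is non-random, e.g. by site or time | Not stated | Not stated; a common distribution fits a random split better |
| Linked to the internal validation step | Yes | No: the validation section does not mention it |

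Neither column meets all three rows.

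**Step 3. Do the counts imply a split?** 300 + 420 = 720, which exceeds 600 by 120. If both counts come from the enrolled patients, at least 120 patients belong to both. If they are instead cumulative accrual points, 420 − 300 = 120 patients would be new when validation starts, and a split by time would be possible. The plan states neither reading, and part of the 420 may belong to external validation. The counts therefore do not supply the missing boundary.

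**Step 4. Search of the rest of the plan.** No section names centres, dates or fractions that form a development group and an evaluation group.

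**The case against.** The best reply is that the wording is not exclusive. The plan says that the step relies mainly on methods such as K-fold, and its next sentence speaks of a non-random split. One can read this as an intended split whose boundary was left out, so that the fault is under-specification rather than a wrong method. That reading is fair, but it does not remove the problem: the level is credited to the K-fold-led step, and the boundary is missing on either reading.

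A second reply is that folds could be formed by centre, so that each round has a development part and an evaluation part separated by location. Whether rotating such splits would satisfy the plan's definition is arguable. The plan does not state centre-based folds, so the point here concerns ordinary K-fold only.

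Three stronger readings may tempt a reader, and the documents do not support them:
- **That the plan holds back no data at all.** It names training, validation and test sets, and the test set may lie outside the folds. What is missing is a non-random development and evaluation split.
- **That performance estimates will be biased by some amount.** The documents give no K, no event rate and no internal share of the 420, so no size can be derived.
- **That transferability or routine use rests on this step.** The plan ties those to TRIPOD level 4, reached through external datasets, which this point does not touch.

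**Conclusion.** The point holds in a limited form. The plan credits its internal step with TRIPOD 2b, defines 2b as a non-random split into development and evaluation groups, names a main method that does not by itself give that split, and specifies no such split elsewhere. The conclusion uses only the plan's own definition of 2b and the ordinary meaning of K-fold; it needs no assumption on sample size, event rate or accuracy.

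Its size is a matter of labelling and specification: what may be reported after internal and before external validation. It should be fixed, but at the low end of priority. The reason to act before modelling is practical: once every available case has entered screening, tuning or refitting, no untouched group can be recovered from those data.

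**What to change.** Choose one of two changes before modelling starts.

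**(a) Remove the 2b statement.** Describe the internal step as resampling-based validation by K-fold, kept separate from (nested around) any K-fold used for tuning. This changes little beyond wording; the cost is that the 2b label is given up.

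**(b) Keep 2b and specify the split.** Name the centre or centres, or the enrolment-date cut-off, that form a locked evaluation group.
- Keep that group out of the univariate feature screening, which WP3 at present runs over all collected data, and out of tuning and re-specification.
- Judge suboptimal performance, and retrain, by K-fold within the development group only.
- Evaluate the final model once on the locked group, and report 2b from that evaluation alone.
- State that a model which fails there and is then retrained may not be reported as 2b on the same group.

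Both kinds of split look workable: several centres contribute patient data, and enrolment (months 1–30) overlaps modelling (months 12–32). The cost is fewer cases for training and a less precise performance estimate than one using all cases. Group sizes should be set from the analysable cases available; the plan's counts of 300, 420 and 600 are not like for like and should not be used for this directly.

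Under either option, state whether the test set in Statistical analysis methodology is this evaluation group or a separate set.

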The Wilcoxon Mann-Whitney (WMW) test will be used to investigate the ability of these features to predict clinical outcomes on univariate analysis, and the feature showing the lowest p-value will be considered as the most predictive parameter. Receiver Operating Feature curve analysis (ROC) will also be performed on the most significant feature obtained at WMW analysis, calculating the area under the curve (AUC) with the corresponding 95% confidence interval (CI) according to the Clopper-Pearson method. Model processing will be performed through advanced ML and AI techniques first on a dedicated training dataset to fit the model parameters. The obtained hyperparameters will be tuned on a dedicated validation dataset and finally a test dataset will be employed as a dataset independent of the training dataset but following the same probability distribution.

Predictive model development

The objective of the second phase is creating multiple distinct but modular multivariate models, trained through advanced ML and AI techniques and segmented into specific modular areas of interest (T.3.2).

Different supervised models will be developed including logistic regression, decision tree, support vector machine, random forest, XGBoost classifier, and artificial neural networks. The k-fold cross-validation will be used for hyperparameters tuning. The final step in the proposed methodology is the statistical significance comparison of the performance of the ML models. This will be done evaluating predictive performances in terms of different metrics: the first evaluation will be based on accuracy (number of subjects correctly classified on the total number of patients) while the other will be on precision (true positive on total test positive), recall (sensitivity), F1 score (2*precision*recall/(precision+recall)) and AUC-ROC.

We estimate about 300 NSCLC cases with complete data to start developing the models. Specific care will be taken to always ensure both user friendliness and model explainability as primary pillars of the model development strategies. Easily interpretable values such as SHAP (SHapley Additive exPlanations) values will be attached to each model in order to avoid any black-box approaches that might render model outputs, difficult to explain to the patients during their interactions with the clinicians.

Predictive model validation

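### K-fold cross-validation both tunes and internally validates the models, retraining has no pass mark or limit, and the named test data are not shielded from either, so internal performance is likely to be optimistic

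*Combined protocol and SAP*

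**What the plan says.** Tuning is described twice. STATISTICAL ANALYSIS METHODOLOGY says "The obtained hyperparameters will be tuned on a dedicated validation dataset". Predictive model development says "The k-fold cross-validation will be used for hyperparameters tuning".

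Under Predictive model validation, "The internal validation step will be focused mainly on techniques such as K-fold cross validation". The plan states that this achieves TRIPOD level 2b and then describes that level as a non-random division of the data, for example by location or time, into two groups: "one to develop the prediction model and the remaining dataset to evaluate its predictive performance".

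The loop comes next. If performance is inadequate, "all the failing models will be reverted back to the previous stage and the models will be retrained with new specifications". Predictive model development lists five metrics (accuracy, precision, recall, F1 and AUC) and six algorithms. It names no primary metric and no pass mark.

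Evaluation data are named. STATISTICAL ANALYSIS METHODOLOGY says "finally a test dataset will be employed as a dataset independent of the training dataset but following the same probability distribution". Predictive model validation adds external datasets after the loop. No size, source, lock or single-use rule is given for either, and the validation section does not mention the test dataset again.

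The counts are about 240 patients for feature screening (WP3, run on everything collected), about 300 complete cases to start development, about "420 NSCLC cases to start the validation process" (internal and external together), and 600 to be enrolled.

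**The concern.** A cross-validated score that chose the hyperparameters is not an unbiased estimate of the chosen model's performance. Unless tuning sits in inner folds and estimation in outer folds, selection and estimation share the same data.

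The retraining loop adds to this. Each return to the previous stage is another look. If retrained versions are scored on the same patients until one looks acceptable, the score that passes is partly a selected maximum. No rule limits the number of looks or fixes what counts as acceptable, and with five metrics the criterion itself can move.

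Feature screening on all collected data is a third route by which evaluation patients can influence the model.

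Predictive model validation links this pathway to use in clinical routine. The models that go forward to external validation are those that came through the loop, so an optimistic internal estimate can carry weak models forward and overstate their robustness.

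**Working it through.** **The plan's own figures.** The plan gives no performance figure to reproduce. Its one computed number, 600 patients at 5% alpha and 90% power, comes without an effect size, test or sidedness. This point does not depend on it.

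**Step 1: the texts side by side.**
- Tuning: a dedicated validation dataset in one section, k-fold in the next. These are different procedures.
- Internal validation: k-fold again, with no mention of nesting.
- TRIPOD 2b: claimed through k-fold, but described as a split by location or time. Ordinary k-fold rotates every case through training and evaluation, so it is not that split.
- Test dataset: independent of the training data. Independence from screening, tuning or retraining is not stated.
- Retraining: no trigger value, no maximum number of cycles, and no statement of which patients score the retrained model.

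**Step 2: what the counts allow.** Two readings are possible.
- Separate pools drawn from the 600: 300 + 420 − 600 = 120 patients at least in both, so at most 420 − 120 = 300 validation patients are new.
- Cumulative milestones (240, 300, 420, 600): 420 − 300 = 120 patients are new when validation starts, up to 300 have already been used in development, and 600 − 420 = 180 come later.

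Both counts are worded as numbers needed to start a stage, which favours the cumulative reading without settling it. The illustration therefore uses both n = 120 and n = 300.

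**Step 3: size of the optimism (illustration).** Assumed, not in the documents: true AUC A = 0.70 for every version, 30% events, correlation ρ = 0.5 to 0.8 between looks, retraining that brings no real gain, and the highest AUC reported. The looks are K = 6 (six algorithms, no retraining) and K = 18 (six algorithms, two retraining cycles).

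Hanley-McNeil standard error: SE² = [A(1−A) + (n₁−1)(Q₁−A²) + (n₀−1)(Q₂−A²)] / (n₁n₀), with Q₁ = A/(2−A) = 0.538 and Q₂ = 2A²/(1+A) = 0.576.
- n = 120 (36 events, 84 non-events): SE² = (0.21 + 35×0.0485 + 83×0.0865)/3024 = 0.00300, SE = 0.0548.
- n = 300 (90 events, 210 non-events): SE² = (0.21 + 89×0.0485 + 209×0.0865)/18900 = 0.00120, SE = 0.0346.

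Mean excess of the best of K equally correlated looks = SE × √(1−ρ) × E_K. Here E_K is the expected maximum of K independent standard normals: 1.267 for K = 6 and 1.820 for K = 18. For example, at n = 120, K = 6 and ρ = 0.5: 0.0548 × 0.707 × 1.267 = 0.049.

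| n | K | ρ = 0.8 | ρ = 0.5 |
|---|---|---|---|
| 120 | 6 | 0.031 | 0.049 |
| 120 | 18 | 0.045 | 0.070 |
| 300 | 6 | 0.020 | 0.031 |
| 300 | 18 | 0.028 | 0.044 |

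**Step 4: effect on a pass decision (illustration).** Take a model with true AUC 0.65 and an assumed pass mark of 0.70. On 120 cases the chance of passing is about 19% at one look, 37 to 50% for the best of 6, and 47 to 69% for the best of 18. On 300 cases it is 8%, 19 to 27%, and 26 to 44%.

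Steps 3 and 4 cover repeated looks at one evaluation set. The K = 6 rows reflect the choice among algorithms; only the further rise to K = 18 belongs to the retraining loop. Neither step measures the separate optimism from un-nested k-fold, which would need the data.

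**The case against.** A reader might infer that the plan sets aside no evaluation data, and that the performance it reports will be the best of many looks. The documents do not support either statement. They name a final test dataset independent of the training data, an evaluation group in the description of level 2b, and external datasets. In the order of the text, external validation comes after the loop, and clinical use is tied to TRIPOD 4. On that reading the loop acts on internal performance only, and a truly external result used once would not carry this bias. That re-scoring uses the same patients is implied by the loop, not written.

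Overlap between development and validation patients is also not a defect in itself, because k-fold reuses development patients by design. The least overlap (120) and the number of new patients (also 120) come from different readings of the counts and should not be combined.

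The AUC figures rest almost entirely on assumptions: retraining may really improve a model, and the plan does not say that the highest AUC will be reported.

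All of this stands, and it limits the point to a risk to internal estimates. It does not remove the point. The test dataset is called independent of training data only, external validation is worded as a possibility, and neither is kept apart from screening, tuning or retraining.

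**Conclusion.** The concern holds for internal performance. Followed as written, un-nested k-fold for both tuning and validation, an unlimited retraining loop without a criterion, and screening on all collected data are likely to give optimistic internal estimates. The claim that k-fold achieves TRIPOD 2b conflicts with the plan's own description of that level.

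The size cannot be fixed from the documents. Under the stated assumptions it is a few hundredths of AUC: about 0.02 to 0.05 over 6 looks and 0.03 to 0.07 over 18, across 120 to 300 evaluation cases. That can matter near a pass mark.

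The plan should be changed, but this does not invalidate an external validation that is done once on untouched data.

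**What to change.** 1. Within the development data, use nested cross-validation: inner folds tune, outer folds estimate. Confine the retraining loop to those data.
2. Define the test dataset already named in STATISTICAL ANALYSIS METHODOLOGY as a locked, non-random split by centre or enrolment date, with its size stated. Exclude it from feature screening, tuning and retraining, and score the final model on it once. A split of this kind matches the plan's description of level 2b, but the wording that the test data follow the training distribution would then need amending. If the counts are cumulative milestones, the roughly 180 patients enrolled after validation starts are one option, provided their follow-up is adequate. A held-out centre is another.
3. Name one primary metric, a pass mark and a maximum number of cycles, and report every retraining cycle.
4. Reconcile the two tuning descriptions and the statement that k-fold achieves TRIPOD 2b. State whether 240, 300, 420 and 600 are cumulative.

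**Cost.** Protocol wording and more computation, with no extra patients. Locked patients are lost to training. A late-enrolled set would have shorter follow-up: the work plan collects data to month 30 and ends modelling at month 32, while the listed models and metrics are for classification, so incomplete outcomes would need explicit handling. A held-out centre avoids that problem but gives up that centre's cases for training.
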